7.2.5.3 Breast Ultrasound

Breast ultrasound (US) is particularly helpful in further delineating findings on mammography. All breast ultrasounds will be obtained at the Kirklin Clinic to complement diagnostic mammograms.

Technical considerations of Breast Ultrasonography (The American College of Radiology Practice Guideline for the Performance of a Breast Ultrasound Examination, <http://www.acr.org/~media/52D58307E93E45898B09D4C4D407DD76.pdf>)

1. The breast sonogram should be correlated with clinical signs and/or symptoms and with mammographic and other appropriate breast imaging studies. If sonography has been performed previously, the current examination should be compared with prior sonograms. A lesion or any area of the breast being studied should be viewed in 2 perpendicular projections, and real-time scanning by the interpreter is encouraged.
2. The size of a lesion should be determined by recording its maximal dimensions in at least 2 planes; orthogonal planes are recommended. At least 1 set of images of a lesion should be obtained without calipers.
3. The images should be labeled as to right or left breast, location of lesions, and the orientation of the transducer with respect to the breast (e.g., transverse or longitudinal, radial or antiradial). The location of the lesion should be recorded using clock face notation and distance from the nipple, and/or shown on a diagram of the breast. The length of the transducer face (footprint), usually between 3.5 cm and 5 cm, can be used to estimate the distance from the nipple. Measurements should not be made from the edge of the areola, as areolar width is widely variable.
4. Sonographic features are helpful in characterizing breast masses. These feature categories and their descriptors are listed and exemplified in the ACR Breast Imaging Reporting and Data System® (BIRADS®). The BI-RADS sonographic categories include size, shape, orientation, margin,

echogenicity, lesion boundary, attenuation (e.g., shadowing or enhancement), special cases, vascularity, and surrounding tissue¹²⁰.

5. Elastography, or tissue stiffness assessment, is among the new feature categories applicable to sonographic analysis of masses, to be included in the Associated Findings section in BI-RADS Ultrasound, edition 2. To minimize errors in communication or interpretation, if elastography is performed, the color scales should be annotated to denote hardness or softness.

6. Mass characterization with ultrasonography is highly dependent on technical factors. Breast ultrasound should be performed with a high-resolution scanner. Gain settings, focal zone selections, and fields of view should be optimized to obtain high-quality images. The patient should be positioned to minimize the thickness of the portion of the breast being evaluated. For evaluation of lesions in, on, or just beneath the skin, a stand-off device or thick layer of gel may be helpful

7.2.5.4 Breast Magnetic Resonance Imaging

Breast Magnetic Resonance Imaging (MRI) is required by the protocol.

Technical considerations of Breast MRI (The American College of Radiology Practice Guideline for the Performance of Contrast-Enhanced Magnetic Resonance Imaging [MRI] of the Breast, <http://www.acr.org/~media/2A0EB28EB59041E2825179AFB72EF624.pdf>)

1. Resolution, contrast, and field strength: Although a 1.5T magnet has traditionally been considered a minimum technical requirement because of the relationship between field strength and resolution, improvements in other components of the scanning process have resulted in improved scan quality at lower field strengths. High spatial and temporal resolutions are needed to detect and characterize small abnormalities on MRI. The slice thickness should be 3 mm or less, and in-plane pixel resolution should be 1 mm or less to minimize the problem of volume averaging effects. Optimized contrast between tumor and surrounding tissue is important. When high-resolution images are being obtained, chemical fat suppression is helpful as a method to reduce fat signal while preserving the signal-to-noise ratio. Sole reliance on subtraction imaging for assessment of enhancement may result in misregistration due to patient motion; use of fat suppression is recommended on sequences used to assess contrast enhancement. Protocols may incorporate both fat suppression and subtraction. Motion correction may be helpful in reducing artifacts encountered with image subtraction.

2. Contrast: Gadolinium contrast enhancement is generally needed in the evaluation of breast cancer. Gadolinium contrast should be administered as a bolus with a standard dose of 0.1 mmol/kg followed by a saline flush of at least 10 ml.

3. Scan time: A pre-contrast scan should be obtained. Scan time in relation to contrast injection is extremely important for lesion characterization. Kinetic information should be reported, based on enhancement data determined at specified intervals separated by 4 minutes or less. Imaging sites should have adequately short temporal resolution for accurate capture of lesion kinetics.

4. Examinations should be performed with a dedicated bilateral breast MRI coil.

Tumor markers. Tumor markers alone cannot be used to assess response and will not be routinely obtained in the course of the study. Patients with stage III breast cancer will undergo imaging studies including imaging studies dedicated to identify skeletal metastases (bone scan and/or bone surveys) to confirm absence of metastatic disease.

7.2.6 Response Criteria

7.2.6.1 Evaluation of Target Lesions

Complete Response (CR): Disappearance of all target lesions

Partial Response (PR): At least a 30% decrease in the sum of the longest diameter (LD) of target lesions, taking as reference the baseline sum LD

Progressive Disease (PD): At least a 20% increase in the sum of the LD of target lesions, taking as reference the smallest sum LD recorded since the treatment started or the appearance of one or more new lesions

Stable Disease (SD): Neither sufficient shrinkage to qualify for PR nor sufficient increase to qualify for PD, taking as reference the smallest sum LD since the treatment started

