It is important to ensure accurate clinical and imaging assessment of the tumor to safeguard against progressive disease. In equivocal cases as well as cases of discrepancy between imaging modalities and physical examination, provisions will be made for the use of MRI. Altogether though, patients whose disease cannot be measured and/or accurately followed by mammogram and/or breast ultrasound and/or exceptionally dedicated breast MRI are not eligible for the study. As most responders to neoadjuvant hormonal therapy can be identified within the first 4 months^{14,87}, patients with stable disease after 4 cycles or progressive disease at any time point will be promptly diverted to surgery or cytotoxic chemotherapy at the discretion of the treating physician.

4.8 **Rationale for the Duration of Preoperative Treatment**

The rationale for extending the preoperative investigational therapy beyond 3-4 months relies on 2 prior clinical studies that have shown a sustained and continued benefit by extending neoadjuvant hormonal therapy to 6 months and beyond^{14,86,87}. The efficacy and tolerability of letrozole in combination with bevacizumab has been established in 2 prior clinical trials^{1,2}. Extension of preoperative treatment beyond 6 months is not allowed by the protocol.

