5.4.2 Treatment Phase

The following evaluations and procedures will be performed during the **treatment phase**: (All assessments should be performed within 5 working days of the protocol-specified date).

- Physical examination, vital signs, weight, and performance status on weeks 4, 8, 12, 16, 20 and 24.
- Laboratory assessments: CBC with differential and platelet count, serum chemistries (glucose, BUN, creatinine, total protein, albumin, bilirubin, calcium, alkaline phosphatase, AST, and ALT), and serum electrolytes (Na, K, Cl) on week 1 and at the beginning of each cycle until week 24.
- Lipid panel (cholesterol, triglycerides, HDL, and LDL) in a fasting state (at least 8 hours) should be obtained at least on cycle 2 and, if elevated, repeated on each cycle until recovery to baseline value or grade 1 (see 5.2.2.2 for management of hyperlipidemia and hyperglycemia).

Serum estradiol levels on weeks 4, 12, and 20 in women receiving goserelin.

- Hepatitis panel as clinically indicated.
- Research biopsy (core needle biopsy of the tumor) at week 4 (required).
- Tumor assessments: Ultrasound of the breast will be obtained on week 4, 8, 12, 16, 20 and 24. Mammogram will be obtained on week 24. Additional PET scans or CT of the chest, abdomen, and pelvis, or bone scans are not required during treatment phase except as clinically indicated (see section **7.2 Measurement of Effect**). MRI breast will be obtained at baseline, week 12 and 24.
- Evaluation of the ejection fraction with an echocardiogram/MUGA only as clinically indicated.
- Surgical evaluation at the end of neoadjuvant therapy. **There must be at least 4 weeks between the last dose of everolimus and TRC105 and surgery.** Patients will continue letrozole until the day before surgery.
- Concomitant medication assessment.
- Assessment of adverse events.

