7.2.3 Disease Parameters

Measurable disease. Measurable lesions are defined as those that can be accurately measured in at least one dimension (longest diameter to be recorded) as ≥ 20 mm with conventional techniques (mammogram, breast ultrasound, exceptionally MRI). All tumor measurements must be recorded in millimeters (or decimal fractions of centimeters). Note: Tumor lesions that are situated in a previously irradiated area should not be considered measurable.

Non-measurable disease. All other lesions (or sites of disease), including small lesions (longest diameter < 20 mm with conventional techniques), are considered non-measurable disease. For this protocol it will be satellite lesions in the affected breast.

Target lesions (not applicable for this trial). All measurable lesions up to a maximum of 5 lesions per organ and 10 lesions in total, representative of breast(s) involved, should be identified as **target lesions** and recorded and measured at baseline. Target lesions should be selected on the basis of their size (lesions with the longest diameter) and their suitability for accurate repeated measurements (either by imaging techniques or clinically). A sum of the longest diameter (LD) for all target lesions will be calculated and reported as the baseline sum LD. The baseline sum LD will be used as reference by which to characterize the objective tumor response.

Non-target lesions (not applicable for this trial). All other lesions including any measurable lesions over and above the 10 target lesions should be identified as **non-target lesions** and should also be recorded at baseline. Measurements of these lesions are not required, but the presence or absence of each should be noted throughout follow-up.

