7.2.5 Methods for Evaluation of Measurable Disease

All measurements should be taken and recorded in metric notation using a ruler or calipers. All baseline evaluations should be performed as closely as possible to the beginning of treatment and never more than 4 weeks before the beginning of the treatment.

The same method of assessment and the same technique should be used to characterize each identified and reported lesion at baseline and during follow-up. Evaluation by clinical examination will always be complemented by imaging evaluation. See **Appendix C** for guidelines issued by the American College of Radiology for imaging studies of the breast. In cases of discrepancy between clinical and radiographic evaluation by >1 cm, a complementary imaging technique (breast ultrasound when the mammograms are inconclusive and breast MRI when both mammograms and breast ultrasound are inconclusive) will be used for the initial and subsequent assessments of the target lesion(s).

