7.2.6.3 Evaluation of Best Overall Response

The best overall response is the best response recorded from the start of the treatment until completion of protocol treatment, early termination, or disease progression/recurrence (taking as reference for progressive disease the smallest measurements recorded since the treatment started). The patient's best response assignment will depend on the achievement of both measurement and confirmation criteria.

Target Lesions	Non-Target Lesions	New Lesions	Overall Response	Best Response for this Category Also Requires:
CR	CR	No	CR*	NA for this trial

CR	Non-CR/Non-PD	No	PR**	NA for this trial
PR	Non-PD	No	PR	
SD	Non-PD	No	SD	Documented at least once ≥ 4 wk from baseline
PD	Any	Yes or No	PD	No prior SD, PR or CR
Any	PD***	Yes or No	PD	
Any	Any	Yes	PD	

* For the definition of a pCR please refer to section 7.3.1.3. Definition of pathologic complete remission (pCR). No subsequent confirmation is required for pCR. ** Residual disease persistent in pathology specimen (near pCR if less than 0.5 cm residual disease in the breast)
 
***In exceptional circumstances, unequivocal progression in non-target lesions may be accepted as disease progression.
 
Note: Patients with a global deterioration of health status requiring discontinuation of treatment without objective evidence of disease progression at that time should be reported as “symptomatic deterioration”. Every effort should be made to document the objective progression even after discontinuation of treatment.
				

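### Target-lesion progression is a 20% rise over the smallest reading, with no stated minimum increase or confirmation, so a shrunken lesion of 10-15 mm can be scored as progressive on a 2-3 mm difference

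*Combined protocol and SAP*

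**What the plan says.** Section 7.2.6.1 gives the rule for target-lesion progression: "At least a 20% increase in the sum of the LD of target lesions, taking as reference the smallest sum LD recorded since" treatment started, or a new lesion. Partial response is "At least a 30% decrease in the sum of the longest diameter (LD) of target lesions" relative to baseline. No minimum increase in millimetres is written anywhere in the protocol.

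Section 7.2.6.3 says that "The patient's best response assignment will depend on the achievement of both measurement and confirmation criteria". The progression rows of its table contain no confirmation requirement. Section 7.2.6.2 mentions later confirmation only for progression of non-target lesions.

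Section 5.4.2 sets the schedule: "Ultrasound of the breast will be obtained on week 4, 8, 12, 16, 20 and 24". MRI is at baseline and weeks 12 and 24, and on-treatment mammography is at week 24 only. Ultrasound is therefore the only scheduled imaging at weeks 4, 8, 16 and 20. Under section 7.2.3 a measurable lesion is at least 20 mm and sizes are recorded in millimetres or decimal fractions of a centimetre.

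Section 4.7 states the consequence: patients with "progressive disease at any time point will be promptly diverted to surgery or cytotoxic chemotherapy", at the treating physician's discretion as to which. Section 5.6 instead lists progression among the reasons for which the principal investigator may stop treatment.

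**The concern.** A percentage threshold applied to a shrinking lesion becomes a small number of millimetres. The reference is the lowest of several readings, so a reading that is low by chance sets the bar for every later scan. With monthly ultrasounds, a lesion that has shrunk and then stayed the same size has repeated chances to cross the line through measurement error alone.

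What is at stake is the progression call at each time point and the duration of response, which section 7.2.7 ends at documented progression. Through section 4.7, a false call could also shorten treatment in a patient who is responding. That could affect the pathologic complete remission or downstaging assessed at surgery, which the stage 1 rule in section 4.2 counts.

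**Working it through.** The documents give no measurement error and no false-progression rate, so there is no plan figure to reproduce. The check has two parts.

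**1. Threshold arithmetic.** Increase needed = 0.20 × smallest reading.

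| Baseline | Shrinkage | Smallest reading | Increase needed | Size at the call | Below baseline |
|---|---|---|---|---|---|
| 20 mm | 30% | 14 mm | 2.8 mm | 16.8 mm | 16% |
| 20 mm | 50% | 10 mm | 2.0 mm | 12 mm | 40% |
| 30 mm | 30% | 21 mm | 4.2 mm | 25.2 mm | 16% |
| 30 mm | 50% | 15 mm | 3.0 mm | 18 mm | 40% |
| 50 mm | 50% | 25 mm | 5.0 mm | 30 mm | 40% |

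A 2-3 mm trigger therefore belongs to smallest readings of 10-15 mm (2/0.20 = 10; 3/0.20 = 15). In the series 30, 25, 20, 15, 18 mm, 18/15 = 1.20 meets the rule, while 18/30 = 0.60 is 40% below baseline.

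**2. Chance of a false call.** Monte Carlo, 200,000 runs per cell:
- One lesion, read at baseline and every 4 weeks.
- True size falls linearly to its final value at week 12 and is then constant.
- Progression is called if any reading is at least 1.2 × the smallest earlier reading.
- The reading error is an assumption. It is independent between readings unless stated.

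Results through week 20, the last scheduled scan at which a call can still shorten a 24-week course:

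| Tumor, error SD | 0% shrinkage | 30% | 50% | 60% |
|---|---|---|---|---|
| 30 mm, 1 mm | 0.1% | 1% | 7% | 15% |
| 30 mm, 1.5 mm | 6% | 9% | 24% | 34% |

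For a 50 mm tumor with SD 1.5 mm, the range through week 20 is from near 0 to 11%.

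Sensitivity, through week 24, 30 mm tumor:
- SD 1.5 mm, independent errors: 8, 16, 37 and 51%.
- SD 1.5 mm, correlation 0.5 between readings (assumed): 0.3, 3, 16 and 30%.
- Error proportional to size, CV 8%: about 49% with no change and 23% with 50% shrinkage.

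To show what an absolute minimum does, and not to propose a value: with an illustrative 5 mm minimum, the SD 1.5 mm figures through week 24 go from 8, 16, 37 and 51% to 8, 5, 5 and 5%. It helps shrunken lesions. It leaves an unshrunken 30 mm lesion as it was, because 20% of 30 mm is already 6 mm.

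**The case against.** The strongest reply is that the written sentence may not be the whole rule. Section 7.2.1 says progression will be evaluated by RECIST, and the reference is titled version 1.1. Whether that source sets an absolute minimum cannot be checked from these documents. This stands: what is shown is that the protocol's own text has no minimum. That text is still what site staff will read, and it is not reconciled with the citation.

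Second, there are safeguards. Section 4.7 provides for MRI in equivocal or discrepant cases, calipers are used at each visit, MRI is scheduled at weeks 12 and 24, and section 5.6 leaves discontinuation to judgement. These reduce the risk but do not settle it. Section 4.7 does not define equivocal, and the other imaging check starts only "In cases of discrepancy between clinical and radiographic evaluation by >1 cm, a complementary imaging technique" being used above that difference, so a 2-3 mm change does not by itself trigger it.

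Third, the simulation has limits. Error size and independence are assumed. The no-change case is partly hypothetical, since section 4.7 already diverts stable disease after 4 cycles. Both points stand.

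Several stronger readings are tempting and are not supported:
- **The cells marked not applicable in 7.2.6.3 waive confirmation of progression.** They are in the rows for complete response of target lesions, not the progression rows.
- **Best-response data are corrupted.** The table allows progression as best response only without prior stable disease or response, so an earlier partial response remains the best response.
- **Patients drop out of the primary analysis.** Section 10.2 keeps everyone who received at least one dose in the safety analysis.
- **False progression exceeds true progression on letrozole alone.** The 2.2-12% in section 4.7 are reported rates under unstated criteria, not error-free ones.

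**Conclusion.** The concern holds as a possibility created by the written rule. A lesion with a smallest reading of 10-15 mm can be scored progressive on 2-3 mm while well below baseline, and no confirmation step is stated for that call. A reader might infer that shrunken, stable tumors will generally be scored this way. The documents do not support that, because the size of the problem depends on a measurement error they do not give. Under independent error and a 30 mm tumor, the chance through week 20 runs from 0.1% to 15% at SD 1 mm and from 6% to 34% at SD 1.5 mm. It is lower for larger tumors and correlated errors.

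Nor can one say that the error always grows with depth of response. It does so with a constant SD in these scenarios, but with a constant CV of 8% it is higher with no change (49%) than after 50% shrinkage (23%).

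The effect falls on time-point calls, duration of response and, through section 4.7, possible early loss of treatment and of the pathologic outcome at surgery. It does not fall on best overall response after a prior partial response, or on membership of the safety analysis.

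**What to change.** For the reported response and duration data only, score target-lesion progression when the 20% rise over the smallest sum also exceeds a prespecified absolute increase larger than measurement error. The investigators should set the value and state the measurement error behind it. In 7.2.6.3, delete the sentence on confirmation criteria or state the criteria actually used.

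Separately, reconcile the following on which criteria define progression and which reading counts for diversion:
- section 4.7 (patients will be diverted) with section 5.6 (treatment may be stopped);
- section 7.2.1 and its RECIST reference with the rule written in 7.2.6.1;
- section 7.2.3, which marks target lesions and their summed diameter as not applicable to this trial, with 7.2.6.1, which builds progression on them;
- the imaging check in 7.2.5 with 4.7 and 7.2.6.3.

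No clinical rule is proposed here; that decision belongs to the investigators.

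The cost is protocol wording, with no extra scans. The drawback is that true slow growth of a small lesion is labelled progression somewhat later in the endpoint data.

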7.2.6.2 Evaluation of Non-Target Lesions

Complete Response (CR): Disappearance of all non-target lesions.

Incomplete Response/Stable Disease (SD): Persistence of one or more non-target lesion(s).

Progressive Disease (PD): Appearance of one or more new lesions and/or unequivocal progression of existing non-target lesions

Although a clear progression of “non-target” lesions only is exceptional, the opinion of the treating physician should prevail in such circumstances, and the progression status should be confirmed at a later time by the review panel (or Principal Investigator).

7.2.6.3 Evaluation of Best Overall Response

The best overall response is the best response recorded from the start of the treatment until completion of protocol treatment, early termination, or disease progression/recurrence (taking as reference for progressive disease the smallest measurements recorded since the treatment started). The patient's best response assignment will depend on the achievement of both measurement and confirmation criteria.

Target Lesions	Non-Target Lesions	New Lesions	Overall Response	Best Response for this Category Also Requires:
CR	CR	No	CR*	NA for this trial

CR	Non-CR/Non-PD	No	PR**	NA for this trial
PR	Non-PD	No	PR	
SD	Non-PD	No	SD	Documented at least once ≥ 4 wk from baseline
PD	Any	Yes or No	PD	No prior SD, PR or CR
Any	PD***	Yes or No	PD	
Any	Any	Yes	PD	

* For the definition of a pCR please refer to section 7.3.1.3. Definition of pathologic complete remission (pCR). No subsequent confirmation is required for pCR. ** Residual disease persistent in pathology specimen (near pCR if less than 0.5 cm residual disease in the breast)
 
***In exceptional circumstances, unequivocal progression in non-target lesions may be accepted as disease progression.
 
Note: Patients with a global deterioration of health status requiring discontinuation of treatment without objective evidence of disease progression at that time should be reported as “symptomatic deterioration”. Every effort should be made to document the objective progression even after discontinuation of treatment.
				

